## Statistical Analysis Plan

- P Tumor Assessments/Scans for Solid Tumors: Perform the same tumor assessments/scans obtained at Screening at the end of every 2 cycles (± 7 days) up to Cycle 4. Thereafter tumor assessments and scans may be performed every 3 cycles, or as clinically indicated. See Section 10.16.1, Solid Tumor Assessment/Scans Section 10.16.2 for details. Computed tomography scans obtained before the ICF is signed may be used as the screening tumor scan if done within 28 days of the first dose of TAS-120. A CT scan must be performed within 2 weeks of discontinuation of TAS-120 treatment, if the patient discontinued for reasons other than radiological disease progression. For scheduled tumor assessments thereafter, see Section 10.16.1, Solid Tumor Assessment/Scans, Section 10.16.2 and Section 11.1, Efficacy Assessment for Solid Tumors.
- q TAS-120 Treatment: QOD arm: TAS-120 will be administered orally, once daily, in the morning (Phase 1 Dose Escalation only) with a glass of water on an empty stomach, 3 times a week (Monday, Wednesday, and Friday) between Days 1 through 21 of each cycle. See Section 9.1.1, Treatment Regimen, for TAS-120 dose levels. QD arm: TAS-120 will be administered orally, once daily, in the morning (Phase 1 Dose Escalation only) with a glass of water on an empty stomach, continuously on Days 1 through 21 of each cycle. See Section 9.1.1, Treatment Regimen, for TAS 120 dose levels.
- Tumor Tissue Sampling for PGx Analysis: Previously collected archived tumor tissue samples (PGx samples) from patients with solid tumors must be shipped to the central PGx laboratory designated by the sponsor, after patients have provided informed consent. For Phase 1 Dose Escalation and Phase 1 Expansion, patients can be enrolled before central PGx laboratory confirmation of FGF/FGFR abnormality has been obtained; however, if available, the archived PGx tissue sample should be collected and shipped to the central laboratory after the signing of the ICF. For Phase 2, refer to the Pharmacogenomic Operation Procedure Manual provided by the sponsor.

CCI
Page 26 of 64

Sponsor: Taiho Oncology, Inc. Protocol: TPU-TAS-120-101

Version: 3.3, Phase 1 Dose Escalation Only

## Statistical Analysis Plan

### 5. ENDPOINTS

This study is to evaluate safety, tolerability, PK, pharmocodynamic, and antitumor activity of the TAS-120 in patients with advanced solid tumors. The efficacy, safety, pharmacokinetic and other endpoints in the study are listed below. The detailed information regarding collections and analysis methods is presented in Sections 9, 10, 11, and 12.

### 5.1. SAFETY ENDPOINTS

#### 5.1.1. Adverse Events

An adverse event (AE) is any untoward medical condition that occurs in a patient while participating in this clinical study. Treatment-Emergent AEs (TEAEs) are those AEs that occur from the initiation of TAS-120 administration to 30 days after the last dose of study medication, and do not necessarily have a causal relationship to the use of the study medication. The TEAEs will be summarized.

## 5.1.2. Laboratory Evaluations

Safety laboratory test results will be collected. All applicable hematological and chemistry laboratory parameters will be graded using computer algorithm per numeric ranges defined in the NCI Common Terminology Criteria for Adverse Events (CTCAE), v4.03. The related endpoints include the worst severity grade will be summarized.

### 5.1.3. Vital Signs and Body Weight

Vital signs (blood pressure, heart rate, body temperature, and respiration rate) and body weight will be collected.

### 5.1.4. ECG

The 12-lead resting electrocardiogram (ECG) will be performed. ECG findings including QT Interval, QTcB, QTcF and RR interval will be recorded and described in Section 10.7.

## 5.1.5. Physical Examination

The physical examination will also be performed in the study.

Sponsor: Taiho Oncology, Inc. Protocol: TPU-TAS-120-101

Version: 3.3, Phase 1 Dose Escalation Only

## Statistical Analysis Plan

#### 5.2. PHARMACOKINETIC ENDPOINTS

For Phase 1 Dose Escalation, the PK parameters in blood and urine will be calculated by standard noncompartmental methods. In addition, the accumulation ratio will be also calculated for the last Wednesday of Cycle 1 (QOD arm) or Day 21 (QD arm) after repeated administrations, as applicable. Dose-proportionality of TAS-120 will be evaluated based on linear, power regression analyses, and 1-way analysis of variance.

- Cmax Maximum concentration in plasma
- Tmax Time to reach maximum concentration in plasma
- $AUC_{0.24}$  Area under the concentration-time curve up to 24 hours (QD arm)
- AUC0-48 Area under the concentration-time curve up to 48 hours (QOD arm)
- ullet AUC0-last Area under the concentration-time curve up to the last observable concentration
- AUC0-inf Area under the concentration-time curve up to infinity
- $T_{1/2}$  Terminal half-life time
- RCmax Accumulation ratio calculated based on Cmax
   RAUC Accumulation ratio calculated based on AUC0-last

The following parameters will be calculated on only Day 1.

- MRT Mean residence time
- CL/F Oral clearance
- Vd/F Volume of distribution
- Ae% Urinary excretion rate as % of dose (QOD arm)
- CLr Renal clearance (QOD arm)

### 5.3. PHARMACODYNAMIC ENDPOINTS

For pharmacodynamics evaluations in blood, serum phosphorus and FGF23 will be determined. For the urine pharmacodynamics evaluation, phosphorus and calcium in urine will be determined.

#### 5.4. EFFICACY ENDPOINTS

Tumor measurements using radiological imaging studies will be collected. The investigator will evaluate the imaging studies for tumor response and/or progression. Response assessment will be made based on the Response Evaluation Criteria in Solid Tumors (RECIST) criteria (version 1.1, 2009).

CC

Sponsor: Taiho Oncology, Inc.

Protocol: TPU-TAS-120-101

Version: 3.3, Phase 1 Dose Escalation Only

## Statistical Analysis Plan

The efficacy endpoints in the study are Best Overall Response, overall response rate (ORR), disease control rate (DCR), and duration of response (DR). In addition, time to radiological progression and/or progression-free survival may be explored as appropriate.

Sponsor: Taiho Oncology, Inc. Protocol: TPU-TAS-120-101

Research\*

Version: 3.3, Phase 1 Dose Escalation Only

## Statistical Analysis Plan

## 6. ANALYSIS SETS

The study populations include safety, DLT-evaluable, PK, pharmacodynamic, and efficacy populations.

#### 6.1. SAFETY POPULATION

The safety population will include all patients who received at least 1 dose of TAS-120. This population will be the basis for safety evaluation.

#### 6.2. DLT EVALUABLE POPULATION

The DLT evaluable population will include all patients in Phase 1 Dose Escalation who either experience a DLT during the first cycle of treatment or who complete the first cycle of with at least 80% of planned study medication (TAS-120) administered. MTD determination will be based on this population.

#### 6.3. PK AND PHARMACODYNAMIC POPULATION

The PK and pharmacodynamic population in Phase 1 Dose Escalation will consist of all patients who received TAS-120 and have TAS-120 evaluable plasma and/or urine data. All such patients will be evaluated for PK and pharmacodynamics unless significant protocol deviations have impacted the data or key dosing information is missing. Changes to the procedures, which may impact the quality of PK and pharmacodynamic data, will be considered "PK and pharmacodynamics relevant protocol deviations." Examples include sample processing errors that lead to inaccurate bioanalytical results and/or inaccurate dosing on the day of PK and pharmacodynamic sampling.

### 6.4. EFFICACY POPULATION

The efficacy population will include all patients in the safety population.

### 6.5. PROTOCOL DEVIATIONS

The protocol deviations may include: informed consent errors, not meeting an eligibility criterion, study drug overdose or other incompliance. The details will be included in TPU-TAS-120-101 Protocol Deviation Definition Document. The major protocol deviations may be summarized while the minor protocol deviations will only be listed.

Sponsor: Taiho Oncology, Inc. Protocol: TPU-TAS-120-101

Version: 3.3, Phase 1 Dose Escalation Only

## Statistical Analysis Plan

## 7. GENERAL ASPECTS FOR STATISTICAL ANALYSIS

#### 7.1. GENERAL METHODS

All relevant data will be presented in patient data listings.

All categorical (binary and ordinal) data will be summarized using frequency counts and percentages of patients. Percentage will be calculated using the corresponding treatment group in the study population as the denominator. The continuous variables will be summarized using number of non-missing observation (n), mean, standard deviation (SD), median, minimum and maximum unless otherwise specified. For example, the numbers of events and censorings will be reported for time-to-event analysis. All estimations will include a point estimate and the corresponding 95% confidence interval.

Summary tables will be presented by dosing schedule (i.e., QOD and QD), dose level and overall. Data listings will be ordered by assigned dosing schedule, dose level and patient ID. The dose levels presented in tables and listings for Phase 1 Dose Escalation are:

8 mg QOD, 16 mg QOD, 24 mg QOD, 36 mg QOD, 56 mg QOD, 80 mg QOD, 120 mg QOD, 160 mg QOD, 200 mg QOD, 240 mg QOD;

4 mg QD, 8 mg QD, 16 mg QD, 20 mg QD, 24 mg QD, 36 mg QD, 56 mg QD, 80 mg QD, 120 mg QD, 160 mg QD, 200 mg QD, and 240 mg QD if applicable.

For concomitant medications and adverse events, the cycles are determined based on their start/onset dates. For other collected data, the cycles are determined based on their visit dates.

When there are multiple laboratory records for a scheduled visit, the one closest to the target date (relative to the Day 1 in that cycle) will be used for analysis. If there are two or more records with the same time period to the target date, the later one will be used for analysis. However, the baseline for laboratory test is the defined as the latest laboratory result prior to the first dose of study medication.

All the analyses of safety, efficacy and pharmacodynamics data for this study will be performed using SAS® statistical software package. Version 9.3 or a later version.

Sponsor: Taiho Oncology, Inc. Protocol: TPU-TAS-120-101

Version: 3.3, Phase 1 Dose Escalation Only

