### 4.5. ADMINISTRATION OF STUDY MEDICATION

Each treatment cycle is 21 days in duration. During Phase 1 Dose Escalation, TAS-120 is given to patients in each cohort of escalating doses to determine the MTD.

All patients receive TAS-120 at the assigned dose, orally, once a day, 3 times a week (Monday, Wednesday, and Friday) [QOD] or continuously (once daily dosing [QD]) in 21-day treatment cycles. TAS-120 is taken with a glass of water on an empty stomach (2 hours after and 1 hour before a meal).

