#### 4.6. STUDY PROCEDURES AND FLOWCHART

The study assessments are summarized in Table 2A. A window of  $\pm$  3 days is allowable for study procedures as long as the proper order of procedures and assessments is maintained. The  $\pm$  3 day window does not apply to assessments on Day 1 and on the last Wednesday of Cycle 1 (QOD) or Day 21 of Cycle 1 (QD). A window of  $\pm$  7 days is allowable for computed tomography (CT) scans and follow-up visits. These windows are not applicable during Screening. If any Screening assessments are repeated on Day 1 of Cycle 1.

Sponsor: Taiho Oncology, Inc.

Protocol: TPU-TAS-120-101

Version: 3.0, Phase 1 Dose Escalation Only

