## Statistical Analysis Plan

- h Electrocardiogram (ECG) Evaluation: On Day 1 and on the last Wednesday of Cycle 1 (Phase 1 Dose Escalation only, QOD arm), obtain 2 hours after the TAS-120 dose. On Day 1 and Day 21 of Cycle 1 (Phase 1 Dose Escalation only, QD arm), obtain at 2 hours after the TAS-120 dose. For all subsequent cycles starting with Cycle 3 (Phase 1 Dose Escalation) or Cycle 2 (Phase 1 Expansion and Phase 2), ECG should be performed on Day 1 (± 3 days) of each cycle obtained 2 at hours after the TAS-120 dose, see Section 10.7, Electrocardiogram (ECG) Evaluation.
-  Hematology and Coagulation: Obtain within 24 hours prior to TAS-120 administration on Day 1 of each cycle, and anytime on Day 8 and Day 15 of Cycle 1 and Cycle 2 (± 3 days). Starting with Cycle 3, the Day 8 assessment is no longer required, unless deemed clinically indicated by the investigator. For more details, see Section 10.10.1, Hematology and Coagulation.
- j Serum Chemistry: Obtain within 24 hours prior to TAS-120 administration on Day 1 of each cycle, and anytime on Day 8 and Day 15 of Cycle 1 and Cycle 2 (± 3 days). For more details, see Section 10.10.2. Starting with Cycle 3, the Day 8 assessment is no longer required, unless deemed clinically indicated by the investigator or if previous serum chemistries showed an elevation of phosphorus that required action as specified Section 9.1.1.1.1.
- k PK/Pharmacodynamic Blood Sampling: During Phase 1 Dose Escalation, collect PK/pharmacodynamic blood samples at the following time points on Day 1 and on the last Wednesday of Cycle 1 (QOD) or on Day 1 and Day 21 of Cycle 1 (QD): immediately prior to dosing (0 hour) and postdose at 30 minutes and 1, 2, 3, 4, 6, 8, 12, 24 (QOD and QD), and 48 hours (QOD only). The 48-hour postdose sample (QOD) and the 24-hour postdose sample (QD) must be collected prior to TAS-120 administration on that day. See Section 10.13.1, Pharmacokinetic/Pharmacodynamic Blood Sample Collection.
-  PK Urine Sampling (QOD only): During Phase 1 Dose Escalation, PK urine samples will be collected predose on Day 1 of Cycle 1 and from 0 to 12, 12 to 24, and 24 to 48 hours postdose. The 24- to 48-hour postdose sample (QOD) must be collected prior to TAS-120 administration on Day 3 of Cycle 1. See Section 10.13.2, Pharmacokinetic Urine Sample Collection (QOD Arm Only).

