## 7.2.4. Study Day

The study day in the study is the days relative to the first dose date in the study, while the cycle day is the days relative to the first dose date in that cycle.

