### 10.4. LABORATORY EVALUATIONS

Blood samples for hematology, coagulation and serum chemistry assessments are collected and measured at baseline (within 7 days prior to study medication administration on Day 1 of Cycle 1), within 24 hours prior to Day 1 study drug administration of each cycle, anytime on Day 8 and Day 15 of Cycle 1 and Cycle 2, the end of treatment visit and 30-day safety follow-up visit. Starting with Cycle 3, the Day 8 assessment is not required, unless deemed clinically indicated by the investigator. Creatine kinase needs to be repeated on Day 1 of Cycle 2. Fractionation of CK into its isoforms must be performed in case of an elevation of CK (unless the isoform CK [isoform skeletal and heart muscle] [CK-MM and CK-MB] was tested, in which case a fractionation is no longer needed). If CK is abnormally elevated at Screening (Day -7 to -1), the results of the fractionation must be available prior to starting TAS-120 treatment for that patient.

Hematology and coagulation parameters that will be measured include: RBC count, Hemoglobin, Hematocrit, Platelets, INR, APTT, White blood cell (WBC) count with differential, Neutrophils, Lymphocytes, Monocytes, Eosinophils, Basophils. Serum chemistry parameters that will be measured include: ALT (SGPT), AST (SGOT), Alkaline phosphatase, Total bilirubin, Albumin, Creatinine, Blood urea nitrogen (BUN), Phosphorus, Calcium, Chloride, Sodium, Potassium, Bicarbonate, Glucose, CK, and CRP and ß2-microglobulin for multiple myeloma only. Fractionation of bilirubin (direct/indirect bilirubin or conjugated/unconjugated) must be performed in case of an elevation of total bilirubin.

Sponsor: Taiho Oncology, Inc. Protocol: TPU-TAS-120-101

Version: 3.3, Phase 1 Dose Escalation Only

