# Statistical Analysis Plan

Urine sample for qualitative analysis are only collected at baseline (within 7 days prior to study medication administration on Day 1 of Cycle 1), within 24 hours prior to study medication administration on Day 1 beginning with Cycle 2, the end of treatment visit and 30-day safety follow-up visit. The following parameters will be measured: protein, glucose, and urine density.

The website http://www.globalrph.com/conv\_si.htm provides conversion factors between SI units and Conversion units.

The CTCAE grades of Hemoglobin, Platelet, INR, APTT, White blood cell (WBC) count with differential, Neutrophils, Lymphocytes, Fibrinogen, ALT (SGPT), AST (SGOT), Alkaline phosphatase, Bilirubin, Albumin, Creatinine, Calcium, Sodium, Potassium, and Glucose will be determined using computer algorithm only based on the numerical component of CTCAE v4.03 grading scale. For the parameters with uni-directional criteria, the CTCAE grade will be derived from 0 to 4. For the parameters with bidirectional criteria, the CTCAE grade will be derived from both low and high direction. Grade 0 is defined for a non-missing value which doesn't meet any criteria and within the normal range.

The worst severity grade during the treatment and 30 days follow-up will also be summarized descriptively. For the parameter with bi-directional criteria, both highest and lowest grade will be summarized. The worst grade in cycle 1 also will also be summarized in same way.

The shift in CTCAE grades from baseline to the worst grade in Cycle 1, and Entire Study for bi-directional parameters and unidirectional parameters will be presented. For all lab tests, a shift table in normal range from baseline to the worst grade in Cycle 1, and Entire Study will also be presented.

All collected laboratory hematology, coagulation, serum chemistry and urinalysis results will be listed. The normal laboratory ranges provided by laboratory will be also listed.

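### Dose Escalation SAP: assigning laboratory data by visit date puts a same-day pre-dose Cycle 2 Day 1 sample in Cycle 2, leaving the descriptive Cycle 1 grade tables with no scheduled result after Day 15

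*SAP*

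**What the plan says.** All references are to the Dose Escalation SAP unless another document is named.

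- **Cycle assignment (7.1).** Two rules are given. For events and medications: "For concomitant medications and adverse events, the cycles are determined based on their start/onset dates". For everything else, laboratory data included: "For other collected data, the cycles are determined based on their visit dates".
- **Start of a cycle (7.2.4, 4.5).** "the cycle day is the days relative to the first dose date in that cycle", and "Each treatment cycle is 21 days in duration".
- **Laboratory schedule (10.4, Table 2A).** Blood is drawn "within 24 hours prior to Day 1 study drug administration of each cycle, anytime on Day 8 and Day 15" of Cycles 1 and 2. The Table 2A footnote on hematology and coagulation agrees: "Obtain within 24 hours prior to TAS-120 administration on Day 1 of each cycle". Table 2A marks no hematology, coagulation or chemistry in the column for the last Wednesday or Day 21 of Cycle 1.
- **Window (4.6).** Plus or minus "3 days is allowable for study procedures". The Table 2A footnotes repeat this window for Days 8 and 15.
- **Outputs (10.4).** After describing the worst grade over treatment and follow-up, the SAP adds: "The worst grade in cycle 1 also will also be summarized in same way". It also plans two shift tables from baseline to the worst result in Cycle 1, one by CTCAE grade and one by normal range, each with an entire-study counterpart.

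No sentence attributes a pre-dose C2D1 sample to Cycle 1.

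**The concern.** A sample drawn before the first Cycle 2 dose cannot show an effect of Cycle 2 dosing. It is the only scheduled safety sample that shows the patient's state after Days 16 to 21 of Cycle 1. The visit-date rule nevertheless files it under Cycle 2 when it is drawn on the dosing day, so a table headed Cycle 1 omits the end-of-cycle result.

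The omission works in one direction. Leaving out a draw can lower a patient's worst grade or leave it unchanged, but cannot raise it. It also depends on the calendar. A patient whose second cycle is postponed still has Cycle 1 dates on later samples, while a patient who starts on time does not. The tables therefore compare patients, and possibly dose levels, over unequal stretches of Cycle 1. At stake is how well the descriptive Cycle 1 laboratory tables portray toxicity by dose level.

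**Working it through.** No sample size, power or error rate is involved, and the SAP gives no figure to reproduce. The check is calendar arithmetic on the schedule.

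**Inputs.** Cycle length is 21 days (4.5), so C2D1 is nominally study Day 21 + 1 = 22. The last scheduled safety draw within Cycle 1 is Day 15 (10.4, Table 2A), or Days 12 to 18 with the window (4.6). The C2D1 draw may be taken up to 24 hours before the dose.

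**Step 1. Which cycle receives the C2D1 draw?** Cycle day is counted from the first dose date of the cycle (7.2.4), so a result dated on or after that date belongs to Cycle 2.

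| Draw, Cycle 2 starting on Day 22 | Cycle by date |
|---|---|
| Day 22, before the dose | 2 |
| Day 21, within 24 hours, own date used | 1 |

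The SAP does not say whether a sample drawn the day before carries its own date or that of the C2D1 visit. Under either reading the Day 22 draw goes to Cycle 2.

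**Step 2. Length of the gap.** Days of Cycle 1 after the last scheduled draw = 21 − day of that draw.

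| Day of last draw | Gap | Share of cycle |
|---|---|---|
| 15 (nominal) | 21 − 15 = 6 | 6/21 = 29% |
| 18 (latest) | 21 − 18 = 3 | 3/21 = 14% |
| 12 (earliest) | 21 − 12 = 9 | 9/21 = 43% |

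**Step 3. Delayed Cycle 2.** If the planned Day 22 sample is taken but dosing is postponed, the first Cycle 2 dose date lies later. By date, that sample and any others before the delayed dose fall in Cycle 1.

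**Step 4. With pre-dose C2D1 counted in Cycle 1.** The last scheduled result moves to Day 21 or 22, and the gap falls from 6 days (3 to 9) to 0.

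**Step 5. Other late samples.** Serum phosphorus is also taken for pharmacodynamics on Day 21 (once-daily arm) or the last Wednesday (three-times-weekly arm), per 12.1 and 12.2. The last Wednesday is Day 17, 15 or 20 for a Monday, Wednesday or Friday start. Phosphorus is not in the list of CTCAE-graded parameters in 10.4. It could enter only the normal-range shift, and the SAP does not say that pharmacodynamic values feed that table. Creatine kinase, which 10.4 requires to be repeated on C2D1, would on a same-day draw be absent from the Cycle 1 normal-range shift.

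**The case against.** The strongest reply is that little depends on these tables. DLTs are defined and tabulated separately (4.1.1, 10.2), the MTD rests on the DLT-evaluable population (6.2), and adverse events follow onset dates. The C2D1 value stays in the entire-study tables and in the listings. Dose escalation is complete and, per the protocol, the recommended dose is set. All of this stands, and it limits the point to descriptive outputs.

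The rule also tends to keep the results that matter most: a C2D1 value bad enough to postpone dosing remains in Cycle 1 by date. That is true and reduces the likely understatement, but it is also why delayed and on-time patients are treated unequally.

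Unscheduled or repeat samples dated Days 16 to 21 fall in Cycle 1 as well. This stands in part, because the Dose Escalation SAP does not say whether such results count towards the worst grade. The Phase 1 Expansion and Phase 2 SAPs (6.5.3 in each) do say so. Those SAPs share the visit-date convention, but their laboratory sections plan no Cycle 1 worst-grade table, so the problem does not arise there.

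A reader might also infer that the pre-dose Cycle 1 Day 1 sample contaminates the Cycle 1 worst grade. The documents largely rule this out: 7.1 makes the latest result before the first dose the baseline, and 10.4 takes the worst grade over the treatment and follow-up period.

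**Conclusion.** The point holds for the descriptive Cycle 1 worst-grade and shift tables in 10.4. For patients who start Cycle 2 on time with a same-day pre-dose draw, those tables contain no scheduled hematology, coagulation or chemistry result after Day 15. The gap is nominally 6 of 21 days, and 3 to 9 days with the window. This rests on reading a cycle as starting at its first dose date, which 7.2.4 implies.

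Two stronger readings are tempting and not supported. The first is that DLTs or the MTD are understated because Cycle 1 is the DLT window. They come from separate assessments that do not use this cycle-assignment rule.

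The second is that the understatement can be given as a percentage. With three draws, each having an assumed independent 10% chance of showing a given grade, two draws give 1 − 0.9² = 19.0% and three give 1 − 0.9³ = 27.1%, a difference of 8.1 points. If an abnormality present at one draw is present at all, the difference is 0. The documents give neither the probability nor the correlation between draws, nor how many patients are drawn on the dosing day. Nor do they show that effects accumulating under continuous dosing are hit hardest. The direction is clear and the size is unknown.

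**What to change.** Add to 7.1 or 10.4: for worst-grade and shift tables by cycle, a sample taken before the first dose of cycle n+1 counts as a post-baseline result of cycle n. Cycle 1 then runs from after the first TAS-120 dose through the pre-dose C2D1 sample, or through the last on-treatment sample if Cycle 2 is not started. State that unscheduled results are included. Worded this way, the rule also settles how to treat a sample drawn the day before.

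The cost is one sentence and one programming rule applied to data already collected. Cycle 1 grades may become slightly less favourable. The entire-study tables, DLT outputs and adverse event tables need no change.
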